Screening and Eligibility Assessment: Individuals will be screened by the research study intake coordinator. An initial pre-screen focused on inclusion/exclusion psychiatric diagnoses, medical status, current medication regimen, and ability and willingness to commit to completion of study procedures will be used to initially determine potential study eligibility. Interested individuals will be given a full description of the study procedures and asked to read and sign an IRB-approved informed consent form before participating in a detailed, comprehensive screening and assessment phase. To ensure subjects are not experiencing any acute effects of alcohol, individuals whose breath or saliva alcohol concentration reading exceeds the instruments margin of error (0.002%) will not be allowed to participate until their BAC is not detectable.

Diagnostic/Descriptive Assessment: The *M.I.N.I. International Neuropsychiatric Interview 7.0 for DSM 5* will be used to assess psychiatric and substance use diagnoses, including assessment of opiate use. A medical history will be collected to ensure that the individual is eligible to participate, and the VA medical record may be reviewed to verify medications. In the event that an individual is found to be ineligible, he or she will be given an appropriate referral for further medical or other necessary care. If the individual is eligible, he or she will fill out questionnaires and provide a urine sample to verify self-report of substance use. If female, the urine will first be tested for pregnancy. If the pregnancy test is negative or the individual is male, the urine will be tested for drugs of abuse. A randomization/initial rTMS visit will be scheduled.

Figure 3

rTMS=Repetitive Transcranial Magnetic

Treatment Assignment: Eligible individuals will be randomized to receive active rTMS or sham treatment. Participants will be randomized using a stratified permuted random block design with block sizes of 2 and 4; *this will be utilized to maintain treatment assignment balance throughout the treatment enrollment period based on concomitant pain medication use (yes/no).*

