Community Participation Index	Assess community functioning	X		X
ShortForm36 Health Survey: SF36	Assess quality of life	X		X
Patient Health Questionnaire nine (PHQ9)	Assess depression	X		X
Trait form of the State-Trait-Anxiety Inventory	Assess anxiety symptoms	X		X
Pittsburgh Sleep Quality Index: PSQI	Assess sleep functioning	X		X
Daily Pain Diaries (Numeric Rating Scales; NRS)	Assess pain level	X	X	X
Brief Pain Inventory: BPI	Assess pain severity and functional impairment	X	X	X
McGill Pain Inventory	Assess pain severity	X	X	X
Patient Health Questionnaire: PHQ-15	Assess health status	X		X
Treatment Services Review: TSR	Monitor services utilization	X		X
Best Guess Questionnaire	Assess rTMS blind integrity			
Adverse events	Assess tolerability of rTMS		X	

Data Management: Data will be managed using REDCap as specified in the DMAP.

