Statistical Analysis: *Study feasibility will be primarily measured by a) the total number of rTMS sessions completed (out of 18 total sessions) b) the proportion of participants completing all of the rTMS session and c) the proportion of participants completing all of the rTMS sessions as well as the follow-up visits. Study tolerability will be measured as the total number of treatment emergent adverse events. Group differences (active rTMS vs. sham rTMS) in the feasibility and tolerability measures will be estimated using generalized linear models with appropriate distributions (Negative binomial for session and AE count and logit for study treatment completion). In addition to study feasibility, efficacy measures (opioid use amounts, pain, and sleep quality) will be estimated for the entire cohort as well as estimates of between group differences. Changes in study efficacy outcomes from baseline to follow-up visits will be estimated and analyzed using appropriate statistical approaches. When parametric modeling assumptions can be made, changes over time and associated variability will be estimated between treatment groups using general linear mixed models (GLMMs). The GLMMs will allow us to estimate group-specific changes over time and overall effect sizes, along with the variation in those measures, while controlling for relevant baseline covariates (e.g. baseline craving, morphine equivalents, withdrawal). Although we will likely not be powered to detect between-group differences in binary outcomes (i.e. any drug use), such effects will be explored using generalized mixed models, and for time-to-event data (e.g. days to first opioid use), survival analysis models will be constructed. When parametric modeling assumptions do not appear to be valid, alternative (e.g. non-parametric) approaches will be used. Efficacy outcomes will also be analyzed for evidence of differential treatment effects in subgroups determined by gender, race, and ethnicity. Post-hoc exploratory analyses using GLMMs within the active rTMS group will address whether specific characteristics (e.g. demographics, baseline craving, morphine equivalents, withdrawal, PTSD) are associated with a differential treatment effect. The subgroup-specific treatment effects and corresponding confidence intervals will be constructed and will be interpreted in terms of their clinical, rather than statistical, significance, and effect size of treatment to inform future trials will be estimated.* **Missing Data and Attrition:** *Missing data in longitudinal studies can be a problematic feature but can be mitigated through study design considerations. We will make every effort to prevent attrition, e.g., telephone/text/e-mail reminders prior to visits, and reinforcing attendance at each visit. However, these methods do not ensure that all data will be collected, and appropriate analysis methods will be employed to accommodate missing data. Maximum likelihood estimation yields valid inferences assuming ignorable attrition (i.e., attrition is accounted for by covariates or the dependent variable measured prior to dropout). In addition, in keeping with the ITT, we will make every effort to continue assessments for the entire course of randomized treatment, even among those who stop participating in the study assigned intervention or fail to complete the full rTMS time course.*

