
Sample Size Justification: A total of n=20 participants (n=10 per arm) will be enrolled. We anticipate that <20% of study participants will withdraw from the study or be lost to follow-up, meaning that $\geq n=16$ participants are expected to complete the study. This sample size should allow us to assess feasibility and tolerability of the intervention, and ensure that group-specific changes will be able to be estimated in a precise fashion, with 95% confidence intervals extending ~ 0.5 standard deviation units. Similarly, the overall effect size confidence interval

will likely extend only 0.3 standard deviation units. As an exploratory and developmental project, we recognize that our final sample size will not result in a fully powered study design. Model based means and variability estimates will be derived from unadjusted and adjusted analyses and will be vital for designing a larger, more definitive trial in the context of a subsequent MERIT submission. **Relapse, Drop-Out and Clinical Deterioration:** Every effort will be made to re-engage participants who miss appointments. Clinical deterioration, such as exacerbation of psychiatric or substance use disorders, will be assessed on a case-by-case basis and appropriate care will be arranged. In the case of suicidal ideation, standard STAR program operating procedures will be followed which entails contact of on-call STAR clinicians. Participants will be considered drop outs if they do not come back for follow-up visits after three attempts to contact. With the exception of participants who formally withdraw from the study, we will attempt to assess early terminators at the time of discontinuation and at the post-treatment time points. These participants will be considered in the intent-to-treat efficacy analyses.

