Design Considerations: *Choice of treating participants likely undergoing buprenorphine treatment and using an accelerated (multiple sessions per day) treatment paradigm:* The standard rTMS treatment paradigm in depression is to treat outpatients using one session of rTMS each day, five times per week, for four to six weeks. We considered using this treatment paradigm; however, we chose to use an accelerated paradigm (multiple sessions per day), for the following reasons: 1: If treating outpatients with once daily sessions, there would likely be a great deal of variability in the number of attended sessions per week (OUD patients frequently miss appointments) and a large attrition rate (the opioid relapse rate is high amongst outpatients). 2: Patients are often seen frequently early in treatment (leaving an opportunity for an acute intervention that could easily be applied in other facilities). 3: Our preliminary evidence suggests that rTMS is tolerated while participants are on buprenorphine. *Choice of including participants with co-morbid depressive symptoms:* Because rTMS is known to have an anti-depressant effect we considered excluding patients with concurrent depressive symptoms to avoid the potential confound of improved depression driving anti-pain and anti-craving effects. We chose to include these patients as there is a high rate of comorbid depression in this population (Gros et al., 2013), and excluding these patients would reduce the generalizability of our findings. We will control for depression statistically by including depression as a covariate in analyses. *Consideration of gender as a biological variable:* Though this trial is not powered to detect gender differences, we will perform our analysis using gender as a potential covariate.

Operational Plan and Research Timetable: Funding for two years is requested. The first three months will be used for submitting regulatory documents, staff training and preparing for study initiation. Eighteen months will be needed for patient recruitment and data collection. The final three months will be used for data analysis, dissemination, and MERIT grant submission. At a recruitment rate of approximately 1-2 participants per month, we should have no difficulty in completing the study in the proposed timeframe.

PROTECTION OF HUMAN SUBJECTS

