3. POTENTIAL BENEFITS OF THE PROPOSED RESEARCH TO THE SUBJECT AND OTHERS As rTMS is an FDA approved treatment for depression, and preliminary evidence suggests that it also has anti-pain and anti-craving effects. Research participants receiving active treatment may have improvement in craving, pain, and symptoms of depression. After the study data has been unblinded, we will offer open label treatment to those participants randomized to sham treatment. In addition to the potential direct benefits of participation in this study, participants will help investigators understand the utility of rTMS as a potential treatment for OUD.

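### The depression covariate cannot do the job given to it: the PHQ-9 value to be used is not stated, and a baseline value leaves the route through improved depression untouched (minor; also, no efficacy model names the randomisation stratum)

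*Combined protocol and SAP*

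**What the plan says.** Design Considerations explains that patients with depressive symptoms might have been excluded "to avoid the potential confound of improved depression driving anti-pain and anti-craving effects". They are kept for generalisability, and the safeguard is one sentence: "We will control for depression statistically by including depression as a covariate in analyses". No instrument, time point or model is given.

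Other sections bear on how to read that sentence:

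- Table 1 lists "Patient Health Questionnaire nine (PHQ9") at screening and at the follow-up visits, but not at the TMS sessions. Both a pre-treatment and a post-treatment value will therefore exist.
- Statistical Analysis describes the efficacy mixed models as "controlling for relevant baseline covariates (e.g. baseline craving, morphine equivalents, withdrawal"). The list is open and names neither depression nor the stratum. No mediation analysis is described.
- Protection of Human Subjects, section 3, expects depression to respond: "Research participants receiving active treatment may have improvement in craving, pain, and symptoms of depression".
- Treatment Assignment stratifies the randomisation: "this will be utilized to maintain treatment assignment balance throughout the treatment enrollment period based on concomitant pain medication use (yes/no"). Design Considerations adds only depression and, as a possibility, gender to the covariates.
- Sample Size Justification: "Model based means and variability estimates will be derived from unadjusted and adjusted analyses". These are intended to inform a larger trial.

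**The concern.** The threat the plan names is a change in depression caused by treatment, which then acts on pain or craving. That happens after randomisation, so it is a mediation question. A covariate can mean two different things here:

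- **Baseline PHQ-9.** This adjusts for prognosis and chance imbalance. It cannot touch what happens after treatment starts.
- **Follow-up PHQ-9.** This does condition on the route, but the treatment coefficient is then no longer the total effect. It equals a direct effect only if depression and the outcome share no unmeasured cause.

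At stake is how the adjusted results are interpreted. On the first reading, an effect running wholly through depression could be described as controlled for depression when nothing had been removed. On the second, a genuine pain effect could look smaller than it is. Leaving the time point open also leaves the choice between two estimands until after data are in hand.

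The stratum is a lesser matter: a factor judged important enough to stratify on is normally named in the analysis model.

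**Working it through.** The plan gives no figure on this point to reproduce. From the documents come the PHQ-9 schedule, 10 per arm enrolled, and about 16 completers (8 per arm if losses are equal). Every effect size and correlation below is an assumption.

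**1. Baseline and follow-up adjustment, large sample.** Let T be randomised treatment, D0 baseline depression and U an unmeasured common cause:

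- D1 = 0.6·D0 + a·T + u·U + 0.7·e1
- Y = b·D1 + c·T + u·U + 0.7·e2

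T is independent of D0, so the coefficient on T has expectation c + a·b with or without D0. With a = −0.5, b = 0.5, c = 0, the expected value is −0.25. Simulation with 400,000 records gave −0.253 unadjusted and −0.253 with D0. The two agreed in all six scenarios run.

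With D1 in the model, the coefficient on T is c − a·k, where k = u²/(0.36 + u² + 0.49).

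- u = 0: k = 0, so the direct effect is recovered (simulated −0.003 against a true 0).
- u = 0.5: k = 0.25/1.10 = 0.227. With c = 0 and a = −0.3, −0.5, −0.8 the coefficient is 0.068, 0.114, 0.182 (simulated 0.066, 0.111, 0.179) against a true 0.
- u = 0.5, a = −0.5, c = −0.3: −0.3 + 0.114 = −0.186 (simulated −0.189).
- Adding D0 as well does not help: k = 0.25/0.74 = 0.338, giving 0.169 (simulated 0.166) for a = −0.5, c = 0.

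**2. The same in SD units at n = 20** (8,000 runs, baseline/follow-up PHQ-9 correlation 0.6). Here d is the PHQ-9 improvement and r the within-arm PHQ-9/pain correlation. Case A: the whole effect runs through depression, with total r·d. Case B: true effect 0.50, none through depression, r due to shared causes, so the follow-up-adjusted expectation is 0.50 − r·d.

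| d | r | r·d | A, baseline-adjusted | 0.50 − r·d | B, follow-up-adjusted |
|---|---|---|---|---|---|
| 0.3 | 0.3 | 0.09 | 0.092 | 0.41 | 0.408 |
| 0.3 | 0.5 | 0.15 | 0.149 | 0.35 | 0.352 |
| 0.5 | 0.3 | 0.15 | 0.150 | 0.35 | 0.345 |
| 0.5 | 0.5 | 0.25 | 0.249 | 0.25 | 0.249 |
| 0.8 | 0.3 | 0.24 | 0.239 | 0.26 | 0.255 |
| 0.8 | 0.5 | 0.40 | 0.400 | 0.10 | 0.099 |

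In case B the baseline-adjusted estimate stays at 0.494 to 0.505.

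**3. Precision of PHQ-9 change by arm.** The half-width for the between-arm difference is t(0.975, 2n−2)·√(2(1−ρ))·√(2/n), with n per arm. At ρ = 0.6:

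- n = 10: 2.101 × 0.894 × 0.447 = 0.84 SD
- n = 8: 2.145 × 0.894 × 0.500 = 0.96 SD

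For ρ = 0.5 and 0.7 the values are 0.94 and 0.73 (n = 10), and 1.07 and 0.83 (n = 8).

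**4. Stratum.** Simulated with stratified blocks of 2 and 4, equal strata, outcome correlation 0.6, no treatment effect and 6,000 runs. Figures are mean 95% half-widths without → with the stratum, adjusting for the baseline outcome:

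- Constant stratum effect, 30% of variance, n = 20: 0.765 → 0.730 (just under 5% narrower).
- Higher-baseline stratum moves up by 0.8 SD, n = 20: 0.913 → 0.761 (about 17% narrower).
- Higher-baseline stratum moves down by 0.4 SD: 0.755 → 0.760 (n = 20) and 0.869 → 0.880 (n = 16), slightly wider.
- Stratum unrelated to outcome: 0.770 → 0.775 (n = 20) and 0.884 → 0.894 (n = 16), about 0.6% and 1% wider.

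In a single-follow-up regression with six independent covariates (the five the plan mentions plus, by assumption, the baseline outcome), adding an unrelated stratum widens intervals by about 2% at n = 20 and 5% at n = 16.

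Type I error with the stratum omitted was 2.3 to 5.3%. The simulation standard error at 5% is √(0.05 × 0.95/6000) = 0.28 percentage points, so there is no inflation.

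**The case against.** The best defence is that little of what the trial will estimate is affected. The reference to baseline covariates in Statistical Analysis points to baseline PHQ-9, and on that reading randomisation guarantees that the adjusted effect targets the total effect. Unadjusted estimates are planned too, feasibility and tolerability are primary, and the trial has 20 participants. The shrinkage in case B needs both the less likely reading and assumed shared causes. All of this stands, and it sets the severity. It does not rescue the sentence itself, which presents the covariate as the answer to a question that a baseline value cannot address.

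A reader might infer more than the documents support:

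- That the plan never says when depression is measured. Table 1 does; what is missing is which value enters the model.
- That the plan adjusts for a post-randomisation variable and so biases the treatment effect. The text does not say so, and its reference to baseline covariates points the other way.
- That the stratum has been excluded. The covariate list is open, so it is unnamed.
- That omitting the stratum inflates type I error or can only widen intervals. The figures above contradict both: in some cases the interval without the stratum is the narrower one.

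It can also be said that a mediation analysis in 16 to 20 people would tell us very little. That is correct. Even the simple PHQ-9 comparison has a half-width (0.84 to 0.96 SD) larger than the whole range of improvement assumed here (0.3 to 0.8 SD).

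**Conclusion.** The point holds, as a minor one. On the likelier baseline reading the effect estimate is sound, but the stated control for improved depression is not delivered. This follows from timing alone and does not depend on the assumed values. On the follow-up reading the treatment coefficient is a direct effect only without unmeasured common causes; otherwise the distortion could be appreciable, with 0.50 SD falling to between 0.41 and 0.10 under the assumed ranges. Those sizes are illustrations, since the documents give none of the inputs.

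The stratum omission is a small gap in specification. Whether naming it gains or costs precision depends on how pain-medication use relates to the outcome, which the documents do not tell us.

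The consequence is limited to adjusted efficacy results, and to how they are described when the next trial is designed.

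**What to change.** 1. In Design Considerations, state that baseline (screening) PHQ-9 enters the adjusted efficacy models as a prognostic covariate, and remove the implication that it controls for improvement in depression. Name it in Statistical Analysis as well, so that the two sections agree.
2. Report PHQ-9 change by arm with its confidence interval, as description only, and note the expected half-width.
3. If follow-up PHQ-9 is ever adjusted for, label it exploratory mediation, state the assumption of no unmeasured common cause, use an earlier PHQ-9 against later pain (for example one week against four weeks), and say that it will be very imprecise.
4. Add the pain-medication stratum as a fixed effect in the efficacy models, in preference to less relevant optional covariates.

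Items 1 to 3 are changes of wording and reporting; the PHQ-9 is already collected. Item 4 uses a factor already recorded and costs one degree of freedom. If the stratum proves unrelated to the outcome, intervals widen by about 0.6 to 1% with one other covariate, or about 2% (n = 20) to 5% (n = 16) with six, which is a reason to keep the covariate list short. The changes should be made before unblinding.

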rTMS. Furthermore, it is well known that in order to derive a meaningful clinical effect, the application of multiple sessions of rTMS are needed. 2: This will be the first trial testing an accelerated rTMS treatment paradigm using established rTMS doses in an addictions population. This is important as there is a clear dose response effect in rTMS, where larger doses of rTMS result in a larger clinical effect ([name] et al., 2010; McDonald et al., 2011). It is additionally important as OUD and other substance use disordered populations may be difficult to treat using the standard treatment paradigm of one session per day over several weeks. 3: This trial will be the first to use rTMS as an adjunct to standard of care opioid treatment. OUD patients, including Veterans, are difficult to engage in outpatient care. Subsequently, a treatment that encourages retention and integration early in the recovery process could have a significant impact on patient outcomes.

RESEARCH DESIGN AND METHODS

Approach Overview (Figure 3): Participants will be recruited from the Ralph H. Johnson VAMC, local VA clinics, and Charleston Center. We will collect data at one week, four weeks, and three months following rTMS completion.

[figure not shown]
Acute Phase: We will screen, consent, enroll, and assess participants during an enrollment session. Following enrollment, each participant will complete baseline measurements of opioid use, opioid craving, pain, and functioning (as outlined below). Following the enrollment session, each participant will be randomized and begin the acute treatment phase of the trial. *Participants will receive a total of six sessions of rTMS on three days during the acute phase of the study over a period of up to three weeks. A period of up to one-week in between treatment days will be allowed to maximize feasibility of intervention deliverability in this population while minimizing risk of a treatment gap that is too long to allow for a summation of effect.* On the third treatment day, pain assessments will be repeated. Craving and pain will be assessed using validated questionnaires.

Continuation Phase: Participants will return at one week, four weeks, and three months for follow-up visits to preliminarily assess the intervention's impact on opioid use, pain, and functional outcomes.

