Recruitment: Participants will be recruited from the Ralph H. Johnson VA Medical Center, other local VA clinics, Charleston Center, and through community and online advertising. Co-I [name] is Medical Director of the STAR program and will assist in participant referrals. CPRS chart review will also be utilized. Approximately four Veterans per month are initiated on buprenorphine medication assisted treatment (MAT), the majority (77%) of which endorse chronic pain. As such, we do not anticipate any issue meeting recruitment goals for this pilot project; however, feasibility of recruitment will be assessed as an aim in this project.

Integration of Study Procedures into Standard Care: Outpatient care for includes a combination of pharmacotherapy, psychotherapy, and social work interventions. Pharmacotherapy consists of medication assisted therapy, typically buprenorphine/naloxone. The study procedures will not interfere with this standard MAT treatment or other interventions. Patients being treated for OUD commonly have co-morbid symptoms of depression and anxiety (Gros et al., 2013); as such, antidepressant treatment will be allowed to enhance generalizability.

Figure 2. Change in pain thresholds ± SEM

[figure not shown]
Inclusion Criteria: 1: Be able to provide informed consent and function at an intellectual level sufficient to allow accurate completion of assessments. 2: Meet moderate to severe DSM-5 criteria for OUD. Individuals may also meet criteria for other substance use disorders (with the exception of alcohol or benzodiazepines), but must identify opioids as their primary substance of abuse. 3: Report chronic pain for at least the past three months and have a Brief Pain Inventory Score ≥ 3 . 4: Participants must be receiving Medication Assisted Treatment (MAT).

Exclusion Criteria: 1: Pregnancy. 2: History of/or current psychotic disorder. 3: History of dementia or other cognitive impairment. 4: Active suicidal ideation, or a suicide attempt within the past 90 days. 5: Contraindications to receiving rTMS (including a history of seizures, or any implanted metal above the neck). 6: Unstable general medical conditions. 7: Current use of tramadol. 8: Active moderate or severe alcohol or benzodiazepine use disorder due to increased risk of seizure.

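### The stated 1-2 participants per month reaches the target of 20 only at about 1.33-1.40 per month or more; the low end gives 14-15 once follow-up is fitted into the 18 months

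*Combined protocol and SAP*

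**What the plan says.** The Operational Plan and Research Timetable divides a two-year award into three blocks.

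- Start-up: "The first three months will be used for submitting regulatory documents, staff training and preparing for study initiation".
- Middle block: "Eighteen months will be needed for patient recruitment and data collection".
- Close-out: "The final three months will be used for data analysis, dissemination, and MERIT grant submission".

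It then concludes: "At a recruitment rate of approximately 1-2 participants per month, we should have no difficulty in completing the study in the proposed timeframe".

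The target is in the Sample Size Justification: "A total of n=20 participants (n=10 per arm) will be enrolled". That section anticipates less than 20% loss, so at least 16 completers. Under Acute Phase, treatment is given "during the acute phase of the study over a period of up to three weeks". Under Approach Overview and Continuation Phase, the last visit is three months after rTMS ends.

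The Recruitment section expects no problem in meeting the goal. It cites about four new buprenorphine starters per month, 77% of them with chronic pain, and adds that "feasibility of recruitment will be assessed as an aim in this project". The Statistical Analysis section begins "Study feasibility will be primarily measured by" and lists three items: sessions completed, completion of all sessions, and completion of all sessions plus follow-up visits.

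**The concern.** The timetable offers a range of rates and treats all of it as comfortable. But the 18 months are not all available for enrolling, because the last participant must still be treated and followed for three months before the analysis block begins. Once that time is taken out, the lower part of the range may not deliver 20.

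What is at stake is mainly precision. The Sample Size Justification ties its interval widths to 20 enrolled and at least 16 completing. If 14 or 15 enrol, interval widths grow by a factor of about √(20/15) = 1.15 to √(20/14) = 1.20. There is also a planning cost. This pilot is meant to inform a larger trial, and a realistic enrolment rate is one of the things that trial will need. The listed feasibility measures all begin after randomisation, so none of them describes recruitment.

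**Working it through.** **Inputs.** Target 20 (Sample Size Justification). Rate 1 to 2 per month, and 18 months for recruitment plus data collection (Operational Plan and Research Timetable). Treatment up to 3 weeks (Acute Phase), which is 3 × 12/52.18 = 0.69 month. Last visit 3 months after treatment (Continuation Phase). Loss 20%, the limit of the stated figure. The documents give no interval from enrolment to first treatment, so it is taken as zero; any real gap would shorten the window.

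**Enrolment window** = 18 − 3 − treatment time.
- Full three weeks of treatment: 18 − 3 − 0.69 = 14.3 months.
- Treatment time ignored: 18 − 3 = 15.0 months.

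Counting the three start-up months, enrolment must close at about month 17.3 to 18.0 of the project.

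**Required rate** = 20 / window: 20/14.3 = 1.40 per month; 20/15.0 = 1.33 per month.

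**Expected enrolment** = rate × window.

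| Rate per month | 14.3-month window | 15.0-month window | 18 months, no follow-up time reserved |
|---|---|---|---|
| 1.0 | 14.3 | 15.0 | 18 |
| 1.5 | 21.5 | 22.5 | 27 |
| 2.0 | 28.6 | 30.0 | 36 |

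The plan gives no derived enrolment figure, so the check is whether each rate reaches 20. At 1.5 and 2.0 per month it does. At 1.0 it does not under any of the three windows, and the third contradicts the plan's own visit schedule.

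**Time needed at 1 per month** = 20 + 3 + 0.69 = 23.7 months, or 23.0 if treatment time is ignored, against 18.

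**Completers at 20% loss:** 14 × 0.8 = 11.2; 15 × 0.8 = 12.0; planned 20 × 0.8 = 16.

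**Against the stated pool.** 4 × 0.77 = 3.08 new starters with chronic pain per month. The required rate is 1.33/3.08 = 43% to 1.40/3.08 = 45% of them. The stated range is 1/3.08 = 32% to 2/3.08 = 65%. Other eligibility criteria and consent reduce the pool; the other recruitment sources enlarge it by an amount that the plan does not give.

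**Chance variation (an assumption).** The documents specify no enrolment process. If arrivals were Poisson at a constant rate with no corrective action, the probability of at least 20 over 14.3 and 15.0 months would be:
- 1.0 per month: 9% and 12.5%
- 1.5 per month: 65% and 73%
- 2.0 per month: 96% and 98%

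**The case against.** The strongest reply is that this is an optimistic remark in a funding timetable, not a calculation that came out wrong. The range is given as approximate, its midpoint yields more than 20, and the required rate lies below that midpoint. The Recruitment section also gives grounds for confidence: about 3.1 new starters with chronic pain per month, plus other VA clinics, Charleston Center, advertising and chart review. Eligibility requires receiving medication-assisted treatment, not newly starting it, so patients already on treatment count too. The study calls itself exploratory and not fully powered, and a shortfall would widen intervals without biasing them.

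Most of that stands. It limits the point to the lower part of the range but does not remove it. The word approximately does not bridge 1.0 and 1.33-1.40, and the extra sources are not quantified.

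A reader might infer that the midpoint rate misses the target about one time in three. That depends on an assumed Poisson process and on the shorter window; with 15.0 months it is nearer one in four. No document sets an assurance level to judge either figure against.

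A reader might also infer that the recruitment aim will go without any estimate. The documents do not support this. Under Protections Against Risks, annual reports to the IRB and VA R&D are to give enrolment rates, and the Statistical Analysis list is introduced as the primary feasibility measures, which leaves room for others. What is missing is a pre-specified recruitment measure in the analysis, not the data.

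**Conclusion.** The point holds for the lower part of the stated range. Below an average of about 1.33 to 1.40 per month, the timetable does not deliver 20 participants followed to three months. A sustained 1 per month gives 14 to 15, or about 11 to 12 completers instead of 16. This assumes a steady rate, no visits in the final three months (which the timetable reserves for analysis and dissemination), and a last participant whose treatment takes between almost no time and three weeks. It does not depend on the Poisson figures.

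It would be wrong to conclude that the trial cannot recruit. The midpoint and the top of the range both reach 20, and the stated pool does not rule out the required rate. The fault lies in giving the same assurance across the whole range. The absence of a recruitment measure from the Statistical Analysis section is a secondary gap in detail.

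**What to change.** In the Operational Plan and Research Timetable, replace the blanket assurance with three figures: the average rate required (at least about 1.4 per month), the month by which enrolment must close (about month 14.3 to 15.0 of the 18, depending on treatment time), and the number expected at 1 per month (14 to 15). Set these against the pool of about 3.1 new starters with chronic pain per month, and say that the other sources are not quantified. If a probability of reaching 20 is quoted, label the Poisson model as an assumption and give the range, for example about 65% to 73% at 1.5 per month.

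As a secondary change, add recruitment to the feasibility measures in the Statistical Analysis section: the enrolment rate already due in the annual reports, and the numbers screened, eligible, consented and randomised, with 95% confidence intervals for the rate and the proportions.

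The cost is a less favourable stated outlook and simple counts. Treatment, visits and the target sample size need not change.
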